## **FORESEEABLE RISKS AND DISCOMFORTS**

Provide a brief description of any foreseeable risks and discomforts to subjects. Include those related to drugs/devices/procedures being studied and/or administered/Performed solely for research purposes. In addition, include psychosocial risks, and risks related to privacy and confidentiality. When applicable, describe risks to a developing fetus or nursing infant.

### **Risks Associated with Neuropsychological and Clinical Assessment/Rating Scales**

Although unlikely, it is possible that during the structured assessment or rating scales, subjects may become distressed when recalling periods of their lives or their current mood state. Subjects may also become frustrated during the neuropsychological testing. Subjects are informed that they can take a break and/or can choose to stop answering questions at any time. To mitigate any risks associated with the neurocognitive assessment or clinical ratings, clinical staff will be available to evaluate and advise the subject during study visits.

### **MR/fMRI/DTI/DKI/MRS**

Currently, there are no known risks associated with fMRI, MRI, DTI/DKI, or MRS scanning in the 3T scanner, however, there are some areas of concern that must be addressed. First, participation in an MRI study requires subjects to be exposed to strong magnetic fields, the long-term effects of which are unknown. The magnetic fields also require caution given the risk of attraction of ferromagnetic metal objects by the high strength magnetic field. Second, some subjects express discomfort by the relatively confined space within the bore of the MR scanner.

Finally, some subjects find the scanning experience unpleasant because of the noise of the gradients during MRI image acquisition. Each of these risks is present for a clinical MR scan, which are not increased by the research project proposed in this application.

### **CBD Administration**

CBD has been shown to have an extremely low side effect profile and since the total amount of THC will not exceed 0.3% by weight, we do not expect significant side effects or psychoactive effects. CBD is not a scheduled substance, and there is no risk of intoxication or addiction to CBD. As with any clinical trial, there are risks of experiencing side effects from the administration of CBD or placebo; these side effects are very rare. Cunha et al. (1980) reported no signs of toxicity or serious side effects; in this two-part, placebo-controlled, double blind study, healthy volunteers were given 3 mg/kg of CBD or placebo per day for 30 days, and patients with epilepsy were given 200-300mg CBD or placebo per day for 4.5 months. The total dose of CBD per day for the current study will be 30mg – thus, we expect no significant side effects. Other studies have reported no adverse effects of CBD in patients with Huntington’s disease, schizophrenia, and Parkinson’s disease after repeated administration (Consroe et al. 1991; Leweke et al. 2012; Zuardi et al. 2006 and 2009). Subjects will have the opportunity to report adverse effects at their weekly check-in visits via direct contact with the PI and study staff. This weekly reporting will reduce the likelihood that subjects experience significant negative side effects for any significant period of time, and the PI as well as they study physician will be reachable by page 24 hours a day 7 days a week.

Sublingual solutions are unlikely to be viewed by the public as analogous to recreational smoked marijuana, thus decreasing the risk of the subject experiencing any potential negative appraisal arising from perceived notions associated with marijuana use while partaking in this study.

The safety of CBD administration in pregnant women and fetuses is unknown. Female participants capable of child-bearing will be asked to provide a sample of urine before the study is begun and at each subsequent study visit in order to screen for pregnancy. If the pregnancy test is positive at any point during the study, the subject will be immediately disqualified and participation in the study will cease. Participation requires that the participant uses contraception methods (such as abstinence, diaphragm, condom, or an intrauterine device) to prevent pregnancy for the duration of the study. The participant will be asked to notify study staff immediately if she misses a period or thinks she might be pregnant. In this case, the participant may have to withdraw from the study.

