A total of 52 (12 in the open-label phase, and 40 in the double-blind phase) female and male participants with anxiety, of minimum age 18, will complete a baseline visit including clinical ratings, an assessment of conventional medication use, quality of life measures, a neuropsychological test battery, a buccal swab sample, and optional neuroimaging (in a subset of participants who are eligible). Participants will subsequently be treated for 6 weeks with the CW sublingual solution. All participants will self-administer 0.5 ml (15 mg of CBD) of solution twice daily (BID). Participants will return to the laboratory or complete remote visits each week to complete clinical ratings and check in with study staff. After 6 weeks of treatment, participants will complete final clinical scales and quality of life measures, a complementary neuropsychological battery, and a corresponding neuroimaging component (where applicable). The open-label phase of the study is expected to take approximately 12 months to complete, and will assess the efficacy of the dose chosen for the double-blind study.

40 female and male participants will be enrolled in the double-blind phase. Study procedures will remain the same as the open-label phase, however participants will receive CW solution or placebo solution in a double-blind, randomized fashion. All participants will self-administer 0.5ml of solution BID for 6 weeks. The double-blind phase of the study is expected to take 24 months to complete.

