### **Double-Blind Trial**

Individuals will be assessed in-person at baseline and weekly for 6 weeks of treatment with compounds administered as sublingual solutions in a double-blind, randomized procedure: subjects will receive either the CW solution or matched placebo. At the weekly visits throughout the treatment period, individuals will complete clinical scales and have a check-in with study staff.

In addition to clinical ratings and a check-in with study staff, neuropsychological testing will be performed at baseline and week 6 in order to assess cognitive performance. Finally, a subset of individuals will receive an hour-long MRI scan at baseline and week 6, with both resting state and task-related functional magnetic resonance imaging (fMRI) in each MRI session. In addition, a brief diffusion tensor imaging (DTI) sequence will also be acquired to examine white matter fiber tract integrity, and magnetic resonance spectroscopy (MRS) will be conducted to examine levels of certain metabolites in the brain. Subjects will also provide a buccal swab sample for genetic analysis at the baseline visit.

[figure not shown]
At the end of the baseline visit, eligible subjects will be randomized to either CW solution or placebo using a standard alternating procedure in accordance with the McLean Pharmacy. Subjects will be instructed on how to administer the compound, as described above.

For both the open-label and double-blind trials, the baseline and the final study visits are estimated to take approximately 3-4 hours, with the weekly visits in the interim estimated to take approximately 1 hour, and 15 minutes for phone check-ins, for a total of approximately 10-12 hours required to complete all possible visits. Urine samples will be collected at every other visit (Visits 1, 3, 5, and 7) to measure THC via GCMS (Quest Diagnostics) and to monitor for the presence of other substances throughout the study. Female subjects will be informed that their sample will also be used to confirm negative pregnancy (HCG) status; if at any point their urine tests positive for HCG, they will be excluded from the study. We are currently in communication with several groups that may be able to assess for CBD in urine; we hope to utilize one of these groups to quantify CBD in urine throughout the study.

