## RECRUITMENT PROCEDURES

Explain in detail the specific methodology that will be used to recruit subjects. Specifically address how, when, where and by whom subjects will be identified and approached about participation. Include any specific recruitment methods used to enhance recruitment of women and minorities.

Recruiting and enrollment will be the responsibility of the McLean study coordinators. Subjects will be recruited from a number of sources, including IRB-approved flyers and post cards, as well as online postings (including Rally) and via RPDR messaging. Medical marijuana certification facilities and anxiety clinics may also refer interested patients to contact the study recruitment line for further screening. Potential subjects for this study must be capable of understanding the nature of this study as well as the discomforts and potential benefits. All subjects will be given as much time as they want to consider their participation in the study and ask any questions they may have before being asked to sign the consent form.

Provide details of remuneration, when applicable. Even when subjects may derive medical benefit from participation, it is often the case that extra hospital visits, meals at the hospital, parking fees or other inconveniences will result in additional out-of-pocket expenses related to study participation. Investigators may wish to consider providing reimbursement for such expenses when funding is available

A tiered payment system will be used for a payment of \$75 at visit 1, \$30 each at visits 2, 3, 4, 5, and 6, and \$75 at visit 7 for a total of \$300; if termination occurs during any point of the visit, subjects are compensated at a rate of \$25 per hour. Subjects who participate in the scanning component of study will receive an additional \$75 at visit 1 and visit 7 for a total of \$450. Subjects will receive a completion bonus of \$50 if they complete the study, for a total of \$350 or \$500, depending on whether they receive MR scanning. Subjects may withdraw from the study at any point; and will still receive payment for the portion of the study they completed at a rate of \$25/hr.

For guidance, refer to the following Partners policies:

Recruitment of Research Subjects

<https://partnershealthcare-public.sharepoint.com/ClinicalResearch/Recruitment%20Of%20Research%20Subjects.pdf>

Guidelines for Advertisements for Recruiting Subjects

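### Pregnancy testing is promised at every study visit, but the procedures collect urine only at Visits 1, 3, 5 and 7

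*Combined protocol and SAP*

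**What the plan says.** Two current parts of the protocol set a schedule for pregnancy testing.

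- **Foreseeable Risks and Discomforts, CBD Administration.** Women who could become pregnant are asked to "provide a sample of urine before the study is begun and at each subsequent study visit in order to screen for pregnancy". The same paragraph says it is not known whether CBD is safe in pregnancy, ends participation on a positive test, requires contraception, and asks for immediate notice of a missed period or suspected pregnancy.
- **Research Design and Methods, Double-Blind Trial.** In a paragraph that opens by covering both phases: "Urine samples will be collected at every other visit (Visits 1, 3, 5, and 7"). The stated purposes are THC measurement and monitoring for other substances. Women are told that "their sample will also be used to confirm negative pregnancy (HCG) status".

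Three other statements bear on what counts as a visit. Recruitment Procedures sets a payment "each at visits 2, 3, 4, 5, and 6". The Double-Blind Trial section says "Individuals will be assessed in-person at baseline and weekly for 6 weeks of treatment", but when it gives visit lengths for both phases it adds "and 15 minutes for phone check-ins". The general description of procedures in Research Design and Methods says "Participants will return to the laboratory or complete remote visits each week", and for the double-blind phase "Study procedures will remain the same as the open-label phase".

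**The concern.** The risk section describes a safeguard that the procedures do not deliver. Staff would work from the visit procedures, and these attach the HCG test to the alternate-visit sample. No visit procedure tells them to collect urine at Visits 2, 4 or 6.

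The test triggers a stopping rule. A positive pregnancy test is an exclusion criterion, and pregnancy during the study is a termination criterion. If the test comes one visit late, a woman on active product takes CBD for another week in a condition whose risk the protocol itself calls unknown. An ethics committee reading the risk section would also believe that testing is more frequent than the procedures provide.

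**Working it through.** No sample-size or power formula applies. The check compares the two schedules on a calendar.

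**Inputs**
- Baseline plus weekly visits for 6 weeks (Double-Blind Trial section), numbered 1 to 7 (Recruitment Procedures).
- Risk-section schedule: every visit.
- Procedures schedule: Visits 1, 3, 5 and 7.
- Assumption: visits fall exactly 7 days apart, so Visit *v* is on day 7 × (*v* − 1).

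| Visit | Day | Risk section | Procedures |
|---|---|---|---|
| 1 | 0 | test | test |
| 2 | 7 | test | none scheduled |
| 3 | 14 | test | test |
| 4 | 21 | test | none scheduled |
| 5 | 28 | test | test |
| 6 | 35 | test | none scheduled |
| 7 | 42 | test | test |

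Taking every other visit out of seven, starting at the first, gives 1, 3, 5 and 7, so the plan's own list is reproduced.

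**Number of tests.** The risk section implies 7 if the pre-study sample is the Visit 1 sample, or 8 if it is separate. The procedures give 4. The shortfall within Visits 1 to 7 is 7 − 4 = 3, at Visits 2, 4 and 6.

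**Interval between tests.** 7 days against 14 days.

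**Extra delay.** For a pregnancy that first tests positive on day *t*, the extra delay is the first procedures test on or after *t* minus the first risk-section test on or after *t*.

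- Days 1–7: day 14 − day 7 = 7 days
- Days 8–14: day 14 − day 14 = 0
- Days 15–21: day 28 − day 21 = 7 days
- Days 22–28: day 28 − day 28 = 0
- Days 29–35: day 42 − day 35 = 7 days
- Days 36–42: day 42 − day 42 = 0

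The delay is therefore 7 days in 3 of the 6 dosing weeks and 0 in the other 3. If the first positive day is uniform over days 1 to 42, the mean is (21 × 7 + 21 × 0)/42 = 3.5 days. In the last affected week the pregnancy is found only at Visit 7, when the 6 weeks of dosing are over.

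**Exposure in a 7-day delay, active product.** At 30 mg per day, 7 × 30 = 210 mg CBD. For an open-label participant who took the optional third daily dose, 7 × 45 = 315 mg.

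The protocol gives neither the number of women who could become pregnant nor a pregnancy rate, so no expected number of late detections can be calculated.

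**The case against.** The strongest reply is that the two texts can both be satisfied. The alternate-visit list exists for THC and substance testing, HCG is an added use of that sample, and the procedures never say that HCG is tested only then. On this reading the risk section supplies the pregnancy schedule and the procedures merely fail to refer to it. That is right as far as it goes: staff who test at every visit comply with both. But the procedures do not tell them to, and they name the alternate-visit sample as the one used for HCG.

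Second, some weekly contacts may be remote or by telephone, so the risk section might mean only visits where urine can be given. The protocol is mixed on remote contact but does not say this. It has double-blind participants seen in person every week, and it pays Visits 2 to 6 alike.

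Third, a figure in the Double-Blind Trial section is not shown and might list further tests. If it did, the practical delay could disappear. The written sentences would still need to be aligned.

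Fourth, the consequence is small. This stands. Seven days is a maximum, other safeguards are in place, and of the 52 planned participants 20 receive placebo, so at most 52 − 20 = 32 people of either sex take CBD.

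Finally, the inconsistency could be removed by weakening the risk section to match the procedures. That would make the texts agree, but it would lower a safeguard already offered where the hazard is stated to be unknown.

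**Conclusion.** The inconsistency is real and minor. If staff follow the procedures as written, a woman who could become pregnant has 4 tests rather than 7, at 14-day rather than 7-day intervals. Detection is 7 days later than the risk section implies in half of the dosing weeks. These figures assume exactly weekly visits, all seven numbered contacts counted as study visits, and no additional testing specified in the figure that is not shown. Contraception, immediate self-reporting and weekly contact limit the harm. Type I error, power, sample size and the efficacy analyses are unaffected.

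**What to change.** Keep the risk section and amend the urine paragraph in the Double-Blind Trial section by adding:

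> *Women capable of child-bearing will also give a urine sample for HCG at Visits 2, 4 and 6; if the visit is remote, they will do a home urine pregnancy test and report the result at that check-in.*

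THC and substance testing can stay at Visits 1, 3, 5 and 7.

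The cost is three extra urine pregnancy tests per woman who could become pregnant, home kits for any remote visit, and one sentence of protocol text. Sample size and analysis do not change.

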### **DNA Collection**

The primary risk of collecting and examining genetic information is the remote possibility of future genetic discrimination. It is possible that these data or the buccal swab samples from which they were derived could be stolen, analyzed, and used to reveal sensitive information that may in turn lead to insurance coverage or employment denial. There is a very remote possibility that enough information could be stolen to help identify a person, exposing individuals to any risks that result as that identification. Procedures described below minimize the possible breach of confidentiality.

**Protection of risks:** To reduce the possible risk of a breach of confidentiality regarding genetic material, the informed consent will include a specific section addressing risks associated with collecting genetic material. The consent form will have choices regarding the permissible uses of his/her DNA. These range from “restriction to this study only” to “any future research use by the study investigators” (provided that any future study is approved by an IRB). One of the choices must be initialed by the participant. Participants will also be informed that they may have their DNA samples destroyed at any time, and will provide the necessary information on how to inform investigators to do this.

## **EXPECTED BENEFITS**

Describe both the expected benefits to individual subjects participating in the research and the importance of the knowledge that may reasonably be expected to result from the study. Provide a brief, realistic summary of potential benefits to subjects, for example, "It is hoped that the treatment will result in a partial reduction in tumor size in at least 25% of the enrolled subjects." Indicate how the results of the study will benefit future patients with the disease/condition being studied and/or society, e.g., through increased knowledge of human physiology or behavior, improved safety, or technological advances.

There may be no direct benefits to the subjects; however, based on previous research, it is reasonable to expect that some subjects may experience an improvement in clinical state or quality of life related to a reduction in anxiety.

It is reasonable to expect that this study will contribute to overall knowledge in this field and potentially provide benefits to society in general through improvements in treatment and management as a result of this increased level of understanding.

Subjects are informed that there may be no direct benefit to them from participating in this study. Subjects may benefit from knowing that the results of this study may improve the future care of people prescribed medicinal marijuana, particularly those with anxiety.

## **EQUITABLE SELECTION OF SUBJECTS**

The risks and benefits of the research must be fairly distributed among the populations that stand to benefit from it. No group of persons, for example, men, women, pregnant women, children, and minorities, should be categorically excluded from the research without a good scientific or ethical reason to do so. Please provide the basis for concluding that the study population is representative of the population that stands to potentially benefit from this research.

No subjects will be excluded on the basis of race, sex, ethnicity or sexual orientation.

When people who do not speak English are excluded from participation in the research, provide the scientific rationale for doing so. Individuals who do not speak English should not be denied participation in research simply because it is inconvenient to translate the consent form in different languages and to have an interpreter present.

All subjects must be native English speakers because several of the cognitive tasks require English as the native language in order to accurately assess cognitive state.

For guidance, refer to the following Partners policy:

Obtaining and Documenting Informed Consent of Subjects who do not Speak English  
[https://partnershealthcare-public.sharepoint.com/ClinicalResearch/Non-English\\_Speaking\\_Subjects.1.10.pdf](https://partnershealthcare-public.sharepoint.com/ClinicalResearch/Non-English_Speaking_Subjects.1.10.pdf)

## RECRUITMENT PROCEDURES

Explain in detail the specific methodology that will be used to recruit subjects. Specifically address how, when, where and by whom subjects will be identified and approached about participation. Include any specific recruitment methods used to enhance recruitment of women and minorities.

Recruiting and enrollment will be the responsibility of the McLean study coordinators. Subjects will be recruited from a number of sources, including IRB-approved flyers and post cards, as well as online postings (including Rally) and via RPDR messaging. Medical marijuana certification facilities and anxiety clinics may also refer interested patients to contact the study recruitment line for further screening. Potential subjects for this study must be capable of understanding the nature of this study as well as the discomforts and potential benefits. All subjects will be given as much time as they want to consider their participation in the study and ask any questions they may have before being asked to sign the consent form.

Provide details of remuneration, when applicable. Even when subjects may derive medical benefit from participation, it is often the case that extra hospital visits, meals at the hospital, parking fees or other inconveniences will result in additional out-of-pocket expenses related to study participation. Investigators may wish to consider providing reimbursement for such expenses when funding is available

A tiered payment system will be used for a payment of \$75 at visit 1, \$30 each at visits 2, 3, 4, 5, and 6, and \$75 at visit 7 for a total of \$300; if termination occurs during any point of the visit, subjects are compensated at a rate of \$25 per hour. Subjects who participate in the scanning component of study will receive an additional \$75 at visit 1 and visit 7 for a total of \$450. Subjects will receive a completion bonus of \$50 if they complete the study, for a total of \$350 or \$500, depending on whether they receive MR scanning. Subjects may withdraw from the study at any point; and will still receive payment for the portion of the study they completed at a rate of \$25/hr.

For guidance, refer to the following Partners policies:

Recruitment of Research Subjects

<https://partnershealthcare-public.sharepoint.com/ClinicalResearch/Recruitment%20Of%20Research%20Subjects.pdf>

Guidelines for Advertisements for Recruiting Subjects

<https://partnershealthcare-public.sharepoint.com/ClinicalResearch/Guidelines%20For%20Advertisements.1.11.pdf>

Remuneration for Research Subjects

<https://partnershealthcare-public.sharepoint.com/ClinicalResearch/Remuneration%20for%20Research%20Subjects.pdf>

